### **8.3 Definition of Baseline**

Baseline will refer to measurements performed during the Pre-Operative Visit (Visit 0).

### **8.4 Data Analysis Conventions**

All data analysis will be performed by [REDACTED]. Statistical programming and analyses will be performed using SAS® version 9.4 or higher. Output will be provided in rich text format (RTF) for tables and portable document format (PDF) for tables, listings, and figures using landscape orientation.

Summaries for continuous and ordinal variables will include the number of observations (n), arithmetic mean, SD, median, minimum, and maximum. Minima and maxima will be reported with the same precision as the raw values; means and medians will be presented to one additional decimal place than reported in the raw values. Standard deviations will be presented to two additional decimal places than reported in the raw values. Summaries for discrete variables will include counts and percentages. All percentages will be rounded to one decimal place (i.e., XX.X%). Differences between test and control treatment groups will be calculated as test minus control and change from baseline will be calculated as follow-up visit minus baseline.

All statistical tests will be one-sided with a significance level of 0.05 ( $\alpha = 0.05$ ), except for the two superiority tests of DCIVA and DCNVA which will be two-sided with a significance level of 0.05. Correspondingly, confidence intervals (CI) for differences between treatment groups will be two-sided at 90% or 95% confidence. All p-values will be rounded to 4 decimal places; p-values less than 0.0001 will be presented as “<0.0001”; p-values greater than 0.9999 will be presented as “>0.9999.”

Unless otherwise specified, summaries will be presented by treatment group and, where appropriate, visit. Listings will be presented by subject number, treatment group, visit/time point, and parameter as applicable.

### **8.5 Adjustments for Multiplicity**

The Type I error rate for the primary effectiveness hypothesis tests will be controlled by requiring all primary effectiveness hypothesis test results to be statistically significant to declare effectiveness success for the study. The overall Type I error rate including the primary and secondary effectiveness hypothesis tests will be controlled by a hierarchical testing strategy in which statistical inference for the secondary effectiveness endpoint will only be performed if the primary effectiveness analyses are successful.

## 9. Disposition of Subjects

The total number of screened subjects and screen failures prior to randomization will be presented. The number of subjects randomized as well as the number and percentage of subjects with at least one eye implanted with an IOL and subjects not implanted with an IOL will be presented by treatment group and overall. Inclusion in the ITT Set, All-Implanted Analysis Set, Best Case Set, Safety Set, [REDACTED]

[REDACTED] as well as study completion status will be summarized by treatment group and for all subjects using discrete summary statistics. The number of discontinuations and reasons for discontinuation will be summarized by treatment group and for all subjects using discrete summary statistics. A subject listing will be provided which includes the study exit date, study completion status, and the reason for premature study discontinuation (if applicable).

In addition, the prevalence of any protocol deviations, major protocol deviations, and minor protocol deviations will be summarized by treatment group and for all subjects using discrete summary statistics. A subject listing will be provided for protocol deviations which will include the date of the deviation, the visit at which the deviation occurred, the deviation code, the deviation description, action taken in response to the protocol deviation, and the classification of whether the deviation was judged to be major or minor in a masked review.

Subject accountability at each of the post-operative visits will be summarized overall for all subjects and by treatment group for first operative eyes and second operative eyes using discrete summary statistics, based on Table A.1 from ISO 11979-7.

Details of the study randomization, including the first eye to be implanted, randomization number, randomization date, randomized treatment, and actual treatment, will also be included within a subject listing.

A subject listing indicating whether a subject met all eligibility criteria, was a screen failure, the screen failure date (if applicable), and the eligibility criteria not met (if applicable) will also be provided.

## 10. Demographic and Baseline Disease Characteristics

### 10.1 Demographic Variables

The demographic variables collected in this study include age, sex, ethnicity, and race. Subjects who record more than one race will be grouped into a single category denoted as multi-racial. Demographic variables will be summarized for the AAS.

Age (years) will be summarized by treatment group and for all subjects using continuous summary statistics. Age will also be categorized as follows: < 65 years and  $\geq$  65 years. Age will be reported in years and calculated using the following formula:

$$\text{Age} = (\text{Informed Consent Date} - \text{Date of Birth}) / 365.25, \text{ truncated as an integer}$$

Age category, sex, ethnicity, and race will be summarized by treatment group discrete summary statistics.

A subject listing that includes all demographic variables will be provided.

## **10.2 Baseline Disease Characteristics**

Baseline clinical parameters will include potential visual acuity (logMAR), target refraction sphere (D), target refraction cylinder (D), target refraction axis (degrees), IOL power calculation (D), axial length (mm), and anterior chamber depth (mm). Baseline clinical parameters will be summarized at the eye level for the AAS by treatment group and for all subjects using continuous summary statistics.

Subject listings for the baseline clinical parameters above, as well as corneal topography and urine pregnancy test results, will be provided.

## **11. Medical History and Concomitant Medications**

### **11.1 Medical History**

Medical history will be coded using Medical Dictionary for Regulatory Activities (MedDRA), Version 24.1.

Ocular and non-ocular medical history will be summarized separately at the subject level by treatment group and overall for all subjects using discrete summary statistics for the Safety Set. If a subject reports the same preferred term (PT) multiple times within the same system organ class (SOC), that PT will only be reported once within that SOC. As with the PT, if a subject reports multiple conditions within the same SOC, that SOC will only be reported once.

Separate listings of ocular and non-ocular medical history will be presented. Ophthalmic pathology of cataract will be excluded from the data listing.

### **11.2 Prior and Concomitant Medications**

Prior and concomitant medications will be coded using World Health Organization Drug Dictionary (WHODrug) Global (B3, September 2021) and summarized to the therapeutic drug class (Anatomical Therapeutic Chemical [ATC] 4 classification) and preferred name. If the ATC 4 classification is not provided, then the next highest classification that is provided in the coding dictionary will be used. The preferred name will be defined as the active ingredient; if the active ingredient is not provided or includes more than two ingredients (e.g., multivitamins), then the drug name will be summarized as the preferred name. Prior to database lock, any uncoded terms will be summarized under the ATC classification and preferred name of “Uncoded.”

Prior medications for a respective eye are defined as those medications that start and stop before the operation for the respective eye. Concomitant medications for a respective eye are defined as those medications listed as having been taken (1) prior to the respective eye IOL implantation and continuing for

any period of time following the respective eye implantation or (2) at any time following IOL implantation.

Ocular and non-ocular concomitant medications will be summarized separately at the subject level by treatment group using discrete summary statistics for the Safety Set. Subjects may have more than one medication per ATC text. At each level of subject summarization, a subject will be counted once if he/she reports one or more medications. Percentages will be based on the number of subjects in each treatment group. In the summaries, ATC classes and preferred names within an ATC class will be presented in alphabetical order. Listings of concomitant medications will be generated separately for ocular and non-ocular data.

## **12. Operative Procedures**

Operative procedure data will be recorded at the operative visit for each eye. The operative parameters include incision size (mm), incision axis (degrees), incision type (corneal, limbal, other), lens extraction method (phacoemulsification, other), capsulotomy shape (continuous curvilinear capsulorhexis, other), position of the haptics (in the bag, partially in the bag, in the sulcus, uncertain), IOL power, whether the subject experienced any intraoperative complications, and whether any SSIs were performed.

Operative procedure variables will be summarized at the eye level by treatment group using discrete or continuous summary statistics, as appropriate, for the Safety Set. A listing of the operative variables will also be provided for each subject for each eye.

## **13. Effectiveness Analyses**

### **13.1 Primary Analyses**

The co-primary effectiveness endpoints are:

- Photopic monocular logMAR best corrected distance visual acuity (BCDVA) in first operative eyes at Month 6 (Visit 4)
- Photopic monocular logMAR near visual acuity with distance correction (DCNVA) in first operative eyes at Month 6 (Visit 4)

The primary analyses of the primary effectiveness endpoints will be based on the AAS with intercurrent events handled using the primary strategy presented in [Section 8.2](#).

If a subject has no observed data for an endpoint at any of the scheduled visits (e.g. subject exits study prior to Month 1 [Visit 3A] study visit and therefore has no DCNVA data), the endpoint will be imputed at the earliest scheduled visit as a normal random variable with mean equal to the respective treatment group mean and SD equal to the respective treatment group SD based on observed data for the respective treatment group at the earliest scheduled visit for that endpoint. If the imputed value is less than the minimum observed value within the respective treatment group or greater than the maximum observed

value within the respective treatment group, the imputed value will be set equal to the minimum or maximum value, respectively. This initial imputation procedure will be performed for BCDVA using SAS® code similar to the code below:

```

proc means data = indata noprint;
  var base;
  by trt;
  output out = A3_stats(drop = _TYPE_ _FREQ_) mean = mean std
= sd min = min max = max;
run;

data indata(drop = mean sd min max Z);
  call streaminit(938428);
  merge indata indata_stats;
  by trt;

  if cmiss(base, aval_v2, aval_v3, aval_v4, aval_v5) = 5 then
do;
  Z = round(rand('Normal', mean, sd), 0.02);
  if Z > max then Z = max;
  else if Z < min then Z = min;
  base = Z;
end;
run;

```

where

- trt = treatment group coded as 1 for the test IOL and 2 for the control IOL
- base = BCDVA at baseline
- aval\_vi = BCDVA at Visit i, i = 2, 3, 4, and 5.

Similar code as above will be used for DCNVA with "base" replace by "aval\_v3" in the means procedure block of code and the data step cmiss if-condition updated to "if cmiss(aval\_v3, aval\_v4, aval\_v5) = 3" and clause "base = Z" updated to "aval\_v3 = Z".

Non-monotone missing data for BCDVA will first be multiply imputed using treatment-based MCMC methodology similarly as in the SAS® code below:

```

/* Impute non-monotone missing data using treatment-based MCMC
for the first operative eye*/
proc mi data = indata out = mcmc nimpute = 30 seed = 891567 round
= 0.02;
  by trt;
  mcmc impute = monotone;
  var base aval_v2 aval_v3 aval_v4 aval_v5;
run;

```

Similar code as above will be used for DCNVA with the variables in the var statement updated to "aval\_v3 aval\_v4 aval\_v5".

Monotone missing data will be imputed for BCDVA using treatment-based re

BCDVA using SAS® code similar to the code below:

```
/* Treatment-based monotone regression imputation */
proc mi data = mcmc out = mi n impute = 1 seed = 891568 round =
0.02;
  by trt _imputation_;
  var base aval_v2 aval_v3 aval_v4 aval_v5;
  MONOTONE REG(aval_v2 = base);
  MONOTONE REG(aval_v3 = aval_v2 base);
  MONOTONE REG(aval_v4 = aval_v3 aval_v2 base);
  MONOTONE REG(aval_v5 = aval_v4 aval_v3 aval_v2 base);

run;
```

After imputation of non-monotone missing data, the DCNVA data will be partitioned into a dataset containing missing data due to withdrawal due to physician decision and a data set containing the remaining DCNVA data, including missing data due to any other reason:

```
/* Split mcmc into cases where missing is due to withdrawal due
to physician decision or other */
data mcmc1;
  set mcmc (where = (DSDECOD ne "Physician Decision"));
run;

data mcmc2;
  set mcmc (where = (DSDECOD = "Physician Decision"));
run;
```

where

- DSDECOD = reason for discontinuation.

The monotone missing data not due to withdrawal due to physician decision will be imputed using treatment-based regression methodology using SAS® code similar to the code below:

```
/* Impute missing data not due to Physician Decision using
treatment-based regression methodology */
proc sort data = mcmc1;
  by PARAMCD &trt. _imputation_;
run;

proc mi data = mcmc1 out = mil n impute = 1 seed = 891568 round =
0.02;
  by PARAMCD &trt. _Imputation_;
  var aval_v3 aval_v4 aval_v5;
  monotone reg(aval_v4 = aval_v3);
  monotone reg(aval_v5 = aval_v4 aval_v3);

run;
```

The resulting imputed data will then be combined with the missing data due to withdrawal due to physician decision. If there is any missing data due to withdrawal due to physician decision, it will be imputed using control-based regression methodology using SAS® code similar to the code below:

```

data mcmc2;
  set mil mcmc2;
run;

proc sort data = mcmc2;
  by _imputation_;
run;

/* Control-based monotone regression imputation */
proc mi data = mcmc out = mi nimpute = 1 seed = 891568 round =
0.02;
  by _imputation_;
  class trt;
  var base aval_v3 aval_v4 aval_v5;
  MONOTONE REG(aval_v4 = aval_v3);
  MONOTONE REG(aval_v5 = aval_v4 aval_v3);
  MNAR MODEL(aval_v4 aval_v5 / MODELOBS=(trt= "2"));
run;

```

Thirty complete datasets will be generated from the above code.

A two-sample t-test will be performed for each imputed dataset and the results of the t-tests will be pooled using PROC MIANALYZE. SAS® code similar to the code below will be used to perform the primary analysis for each imputed dataset and then combine inferences across the imputed datasets:

```

proc sort data = mi;
  by _imputation_;
run;

ods output statistics = stat1(where = (Method ne
"Satterthwaite"));
proc ttest data = mi alpha = α
  by _imputation_;
  class trt;
  var aval_v4;
run;

proc sort data = stat1;
  by class _imputation_;
run;

ods output ParameterEstimates = pes;
proc mianalyze data = stat1 alpha = &alpha theta0 = &theta0;
  modeleffects Mean;
  stderr STDERR;
  by class;
run;

```

where

- $\&\alpha$ lpha = the significance level; 0.10 for BCDVA and 0.05 for DCNVA

- $\theta_0$  = the assumed difference in population means under the null hypothesis, 0.10 for BCDVA and 0 for DCNVA

After pooling the statistical analyses across the imputation datasets, the output dataset resulting from PROC MIANALYZE will contain means and standard errors for each treatment group and for the difference in treatment groups (test minus control), a CI for the treatment group difference (90% CI for BCDVA and 95% CI for DCNVA), and a two-sided p-value testing for whether the difference in treatment group means equals 0. These statistics from PROC MIANALYZE will comprise the primary effectiveness analyses for the primary effectiveness endpoints. If the upper confidence limit of the 90% confidence interval for the difference in treatment group means for BCDVA at Month 6 (Visit 4) is less than 0.1, then  $H_{0e}$  will be rejected in favor of  $H_{1e}$ , and the FINEVISION HP IOL will be considered to be statistically non-inferior to the AcrySof® SN60AT [REDACTED] IOL in BCDVA. If the two-sided p-value < 0.05 in favor of FINEVISION HP IOL for DCNVA at Month 6 (Visit 4), then the FINEVISION HP IOL will be considered to be statistically superior to the AcrySof® SN60AT [REDACTED] IOL in DCNVA.

The study will be considered a success only if both primary effectiveness endpoints are met.

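### The DCNVA (and DCIVA) imputation regressions use none of the same eye's BCDVA; this matters mainly for eyes that leave before Visit 3, and the likely bias is small

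*SAP*

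**What the plan says.** SAP 13.1 imputes BCDVA from that endpoint's full history: baseline ("base = BCDVA at baseline") and later visits ("BCDVA at Visit i, i = 2, 3, 4, and 5"). DCNVA is handled differently.

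- **MCMC step:** "Similar code as above will be used for DCNVA with the variables in the var statement updated to" the three DCNVA values at Visits 3, 4 and 5, by arm.
- **Treatment-based regression step:** the variable list is "var aval_v3 aval_v4 aval_v5". Month 6 is regressed on Visit 3 DCNVA, and Month 12 on the Month 6 and Visit 3 values.
- **Control-based step (physician-decision withdrawals):** the list is "var base aval_v3 aval_v4 aval_v5", so `base` appears. The Month 6 regression, "MONOTONE REG(aval_v4 = aval_v3", has no further predictor, and the Month 12 regression does not use `base` either.
- **Eyes with no DCNVA:** the SAP's own example is a case where the "subject exits study prior to Month 1 [Visit 3A] study visit and therefore has no DCNVA data". Visit 3 DCNVA is then one normal draw from the arm's observed mean and SD, limited to the arm's observed range. It is made once, before the 30 imputations.

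The All-Implanted Analysis Set (SAP 7.2) requires only one postoperative visit, so these eyes are in the primary analysis. SAP 13.2 repeats the DCNVA analysis for DCIVA.

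**The concern.** SAP 8.2 treats all missing DCNVA as missing at random except after physician-decision withdrawal. That assumption is conditional on the variables in the imputation model. DCNVA is near acuity read through the distance correction, so a link with BCDVA in the same eye is plausible. If loss also depends on BCDVA, a model without BCDVA does not meet its own assumption. Imputed near acuity is then too good in the arm whose leavers saw worse.

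No planned DCNVA analysis would show this. The worst-half sensitivity analysis (SAP 13.1.1) is for BCDVA only, and the ITT and Best Case analyses (SAP 13.1.2 and 13.1.3) reuse the same imputation model. At stake are the accuracy of a co-primary estimate and, through SAP 13.2, of the secondary one.

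**Working it through.** **The plan's own figure.** Inputs from SAP 5.1.2: 300 and 150 eyes, difference -0.10, SD 0.14, two-sided alpha 0.05. SE = 0.14 × √(1/300 + 1/150) = 0.0140; noncentrality = 0.10/0.0140 = 7.14; power = 99.99999%. The stated figure of more than 99% is reproduced. The documents give no figure that depends on the imputation predictors, so the rest uses assumptions.

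**Bias from eyes leaving before Visit 3.**

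- From the SAP: 334 and 167 eyes (section 5); SD 0.10 for BCDVA (5.1.1) and 0.14 for DCNVA (5.1.2).
- Assumed: 2% or 5% leave each arm before Visit 3; test leavers' BCDVA is 0.2 logMAR worse than that of stayers, control leavers' is not; within-arm BCDVA–DCNVA correlation ρ is 0.3, 0.5 or 0.7.
- Leavers' DCNVA deficit = ρ × (0.14/0.10) × 0.20.
- The starting draw sets leavers to the arm mean, so bias = -(fraction leaving) × deficit.

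| ρ | Deficit | Bias at 2% | Bias at 5% |
|---|---|---|---|
| 0.3 | 0.084 | -0.0017 | -0.0042 |
| 0.5 | 0.140 | -0.0028 | -0.0070 |
| 0.7 | 0.196 | -0.0039 | -0.0098 |

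A simulation of 2000 runs per setting gave -0.0016, -0.0028 and -0.0039 at 2%, and -0.0042, -0.0070 and -0.0097 at 5%. With Visit 3 DCNVA imputed from BCDVA, the bias was zero to within 0.0001.

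The SE with 334 and 167 eyes is 0.14 × √(1/334 + 1/167) = 0.0133, so the largest bias is 0.0098/0.0133 = 0.74 SE. If that bias were taken off a difference of 0.10, 0.0902/0.0133 = 6.8 SE would remain.

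**Early against later leavers.** A second simulation (1000 trials per setting, 10 imputations) put 10% missing in each arm, with test-arm loss driven by poor BCDVA. It assumed ρ of 0.3 to 0.5 and a Visit 3 to Visit 4 DCNVA correlation of 0.7.

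- Bias was -0.006 to -0.014 for loss before Visit 3, and -0.002 to -0.004 for loss after Visit 3.
- With BCDVA added it was within 0.001 of zero.
- At a true difference of -0.10, power was 1.00 with and without BCDVA.
- At a true difference of zero, false wins for the test lens (nominal 2.5%) were 7.5% to 19% for early loss and 3% to 6% for later loss, against 2% to 3% with BCDVA added.

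The 10% is the SAP's loss over the whole study, so these figures are upper-end.

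**Does adding BCDVA suffice if the starting draw stays?** No. With the same 0.7 correlation, the standardised coefficient of BCDVA in the Visit 4 regression, given Visit 3 DCNVA, is 0.3ρ/(1 - ρ²). The share of bias left is 1 - 0.3/(1 - ρ²), which is 67%, 60% and 41% for ρ of 0.3, 0.5 and 0.7. Simulation agrees: -0.0029, -0.0043 and -0.0041 remain at 5% loss.

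**The case against.** The strongest reply is that this changes no decision, and at the planned effect that stands. With 10% of test eyes missing and an observed difference of -0.10, significance is lost only if each missing eye is about 0.72 logMAR worse than imputed: (0.10 - 1.965 × 0.0140)/0.10.

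Four further points carry weight.

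- **Scope.** A reader might infer that any eye lost with poor distance acuity is imputed blind. The code does not support that. An eye seen at Visit 3 has its Month 6 value predicted from its own Visit 3 DCNVA, and an eye missing only Visit 4 is imputed in the MCMC step from its own Visits 3 and 5. Nor is it literally true that every DCNVA step lists only DCNVA, since the control-based step lists `base`; but its coded regressions do not use it.
- **Mechanism.** Nothing in the documents indicates that leavers differ between arms. The same loss with the same BCDVA deficit in both arms would cancel. Test-arm physician-decision withdrawals get control-based imputation, which works against the test lens.
- **Predictor quality.** An eye that leaves before Visit 2 has only a preoperative BCDVA, measured through the cataract, and one that leaves before Visit 3 has at most a Week 1 value as well. The correlation may be at the low end of the range, and the zero residual bias is built in because simulated loss depends only on BCDVA.
- **Cost.** BCDVA is itself missing in leavers and must be imputed jointly, in an order that suits monotone regression.

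These limit the size of the point. They do not remove it: recorded, relevant data are left out, and no DCNVA sensitivity analysis varies the model.

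**Conclusion.** The gap is real and minor. No coded DCNVA regression contains BCDVA, and the DCIVA analysis inherits this. The main effect is on eyes that leave before Visit 3; for later leavers the bias in the simulation was about a third or less as large.

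Under the assumed 2% to 5% early loss, a 0.2 logMAR BCDVA deficit confined to test-arm leavers and a correlation of 0.3 to 0.7, the bias is about -0.002 to -0.010 logMAR in favour of the test lens, or 2% to 10% of the planned effect. The loss pattern and the correlations are assumptions.

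A reader might go further and infer that the DCNVA superiority claim is unsafe. The documents do not support that: the planned effect is roughly ten times the largest bias in this range. The inflated false-win rates arise only with no true near-vision difference and the whole study's 10% loss falling before Visit 3. The change is worth making because it is cheap and makes the missing-at-random assumption more credible.

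**What to change.** For DCNVA and DCIVA, before unmasking:

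1. Delete the one-off normal starting draw. Preoperative BCDVA decides which eye is operated on first (Protocol 4.1), so practically every eye has at least that value to be imputed from.
2. Include the same eye's BCDVA in the by-arm MCMC and monotone regression steps, in visit order: baseline BCDVA, BCDVA V2, BCDVA V3, DCNVA V3, BCDVA V4, DCNVA V4, BCDVA V5, DCNVA V5. Add a regression for DCNVA V3, so that it is imputed from BCDVA within each of the 30 imputations.
3. Use the same predictors in the control-based step, which also settles the role of `base` there.
4. For DCIVA, use the same order with DCIVA at the visits where the schedule has it measured.

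Steps 1 and 2 belong together: adding BCDVA while keeping the draw leaves about 40% to 70% of the bias.

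The cost is some SAS code and a sentence or two in the SAP. No new data are needed, and the t-test and pooling stay as they are. The downside is a larger imputation model, eight variables instead of three, in which missing BCDVA is imputed jointly; 334 and 167 eyes can support it.

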## 8.2 Missing or Inconclusive Data Handling

Missing data for primary and secondary effectiveness analyses will be imputed under the following strategies.

Nonmonotone missing data will be multiply-imputed using treatment-based Markov chain Monte Carlo (MCMC) methods; monotone missing data will be multiply imputed using regression methods assuming data as either missing at random (MAR) or missing not at random (MNAR) as described below.

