### Primary Strategy

1. Withdrawal due to physician decision: missing data assumed to be MNAR. Control-based multiple imputations will be completed for superiority hypotheses and treatment-based multiple imputations will be completed for non-inferiority hypotheses. [hypothetical strategy]
2. Missing data without withdrawal or withdrawal due to reasons other than due to physician decision: missing data assumed to be MAR. Treatment-based multiple imputations will be completed. [hypothetical strategy]

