  by trt _Imputation_;
  var base aval_v2 aval_v3 aval_v4 aval_v5;
  monotone reg(aval_v2 = base);
  monotone reg(aval_v3 = aval_v2 base);
  monotone reg(aval_v4 = aval_v3 aval_v2 base);
  monotone reg(aval_v5 = aval_v4 aval_v3 aval_v2 base);
run;

```

The resulting imputed data will then be combined with the missing data due to withdrawal due to physician decision. If there is any missing data due to withdrawal due to physician decision, it will be imputed using treatment-based regression methodology, using the worst half of the subjects who have data within the same treatment group, for BCDVA using SAS® code similar to the code below:

```

/* Impute missing data due to Physician Decision
median subjects using regression methodology */
data mcmc2;
  set mil mcmc2;
run;

proc sort data = mcmc2;
  by trt _imputation_;
run;

proc mi data = mcmc2 out = mi2 nimpute = 1 seed = 891568 round =
0.02;
  by trt _imputation_;
  class worse_median_fl;
  var base aval_v2 aval_v3 aval_v4 aval_v5;
  MONOTONE REG(aval_v2 = base);
  MONOTONE REG(aval_v3 = aval_v2 base);
  MONOTONE REG(aval_v4 = aval_v3 aval_v2 base);
  MONOTONE REG(aval_v5 = aval_v4 aval_v3 aval_v2 base);
  MNAR MODEL(aval_v2 aval_v3 aval_v4 aval_v5 /
  MODELOBS=(worse_median_fl = "Y"));
run;

```

where

- worse\_median\_fl = Y if the BCDVA at Month 6 (Visit 4) is greater than or equal to than the treatment group median

The imputed datasets will be analyzed and pooled using the same methodology and summarized similarly as the primary analyses.

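### The DCNVA imputation code in SAP 13.1 does not carry out Section 8.2: the control-based step names the wrong dataset, and eyes with no data get one draw shared by all 30 imputations

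*SAP*

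**What the plan says.** Section 8.2 of the SAP sets two rules for the superiority endpoints. Values lost after a physician-decision withdrawal are taken as MNAR and multiply imputed from control. For the rest: "Missing data without withdrawal or withdrawal due to reasons other than due to physician decision: missing data assumed to be MAR", with treatment-based imputation. It also says that "monotone missing data will be multiply imputed using regression methods". Section 13.1 states that the primary analyses use this strategy.

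For DCNVA, Section 13.1 splits the MCMC output `mcmc` by withdrawal reason into `mcmc1` and `mcmc2`, then imputes `mcmc1` by arm to give `mil`. "The resulting imputed data will then be combined with the missing data due to withdrawal due to physician decision"; the combined file is again called `mcmc2` and is sorted by imputation number. The control-based step follows. Apart from a space, it opens with the line already used for BCDVA, "proc mi data = mcmc out = mi n impute = 1 seed = 891568 round". Its variable list is "var base aval_v3 aval_v4 aval_v5" and its MNAR statement begins "MNAR MODEL(aval_v4 aval_v5". Its output, `mi`, goes to the t-test. The matching step in Section 13.1.1 reads "proc mi data = mcmc2 out = mi2 nimpute = 1 seed = 891568 round".

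For an eye with no observed value of an endpoint, Section 13.1 adds a pre-step: "the endpoint will be imputed at the earliest scheduled visit as a normal random variable with mean equal to the respective treatment group mean", with the SD from the same arm. For DCNVA the earliest visit is Visit 3. The draw is made once, in a data step on `indata`, before the call that creates 30 imputations, and the reason for discontinuation is not consulted.

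Section 13.2 repeats the DCNVA analysis for DCIVA. Section 13.1.2 repeats the primary analyses on the ITT Set, including eyes never implanted. The visible items of Section 19 list neither departure; part of that list is redacted.

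**The concern.** DCNVA is co-primary, and the study succeeds only if both effectiveness endpoints are met. Two features of its code do not match Section 8.2.

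First, if the control-based step reads `mcmc`, the work done on `mil` and `mcmc2` is discarded. Every monotone-missing Visit 4 value in the test arm is then imputed from control, including those that Section 8.2 calls MAR.

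Second, the pre-step is single imputation. The drawn value is identical in all 30 datasets and is treated as observed, so part of its uncertainty is absent from the pooled variance. For a test eye withdrawn by physician decision, the draw comes from the test arm. The MNAR statement covers only Visits 4 and 5, so that test-arm value remains as the regression input.

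At stake are agreement between rule and code on a co-primary endpoint, and a slightly understated standard error. The first feature works against the test lens. The second works slightly for it.

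**Working it through.** **The plan's own figure.** SAP 5.1.2 gives 300 and 150 eyes, a difference of -0.10, SD 0.14 and two-sided alpha 0.05. SE = 0.14 × √(1/300 + 1/150) = 0.0140, and 0.10/0.0140 = 7.14, so power exceeds 99.9999%. The stated figure of more than 99% reproduces. For 99% power a difference of 0.060 would be enough.

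**Tracing the datasets.**

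| | BCDVA, 13.1 | BCDVA, 13.1.1 | DCNVA, 13.1 |
|---|---|---|---|
| Split by withdrawal reason | no | yes | yes |
| Final PROC MI reads | `mcmc` | `mcmc2` | `mcmc` |
| `base` in its VAR list | yes | yes | yes, though no other DCNVA step uses it |

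Reading `mcmc` is right only in the first column. The file comes from a step run by treatment, so it is in treatment order. The DCNVA step runs by imputation number and would be expected to stop.

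**Size if `mcmc` is read.** Let f be the share of test eyes monotone-missing at Visit 4 and b the slope of Visit 4 on Visit 3. Both are assumed. The expected difference is -0.10 × [1 - f(1 - b)].

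| | b = 0 | b = 0.6 | b = 0.8 |
|---|---|---|---|
| `mcmc`, f = 5% | -0.0950 | -0.0980 | -0.0990 |
| `mcmc`, f = 10% | -0.0900 | -0.0960 | -0.0980 |
| Section 8.2, 1% physician-decision | -0.0990 | -0.0996 | -0.0998 |

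Simulation (334/167 eyes, 30 imputations, 1,500 trials per setting) gave -0.0898, -0.0962 and -0.0980 for the middle row. Under no effect, rejection in favour of test was 1.3% to 2.5% with `mcmc` and 2.1% to 2.8% with `mcmc2`, against 2.5% nominal. Control eyes, non-monotone gaps and dropouts after Visit 4 are not affected.

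**Size of the single draw, DCNVA.** Let f now be the share of eyes with no data and r the Visit 3 to Visit 4 correlation, again assumed. Relative to complete data, with many imputations:

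- True variance: 1 + f/(1 - f) + f r². The last term is the noise of the fixed draws.
- Reported variance: 1 + (1 - r²) f/(1 - f).

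For f = 5% and r = 0.8 these are 1.0846 and 1.0190. The ratio is 1.064 and its square root 1.032.

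| No-data eyes | True SE above reported, r = 0.3 | r = 0.8 |
|---|---|---|
| 1% | 0.1% | 0.6% |
| 2% | 0.2% | 1.3% |
| 5% | 0.4% | 3.2% |

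Simulation of the last cell gave an SE ratio of 1.029 to 1.032 with the fixed draw and 0.997 to 1.002 with fresh draws (Monte Carlo error about 0.005).

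**Physician-withdrawn test eye with no data.** An own-arm start followed by the control regression gives an expected Visit 4 value of control mean - 0.10 r. The eye keeps 30% to 80% of the treatment difference for r = 0.3 to 0.8; a control-arm start would keep none. With 1% such eyes the estimate moves by 0.01 × 0.10 × r = 0.0003 to 0.0008 logMAR.

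**DCIVA, only if it is first measured at Visit 4.** The protocol's Schedule of Activities suggests this; the SAP appendix does not settle it. The draw would then be the endpoint itself. The variance ratio is 1/(1 - f) + f, so the true SE is 1.0%, 2.0% or 5.0% larger at f = 1%, 2% or 5%. The one-sided error is 1 - Φ(1.96/√ratio) = 2.6%, 2.7% or 3.1%, against 2.5%. In that case the dataset name does not affect the DCIVA Visit 4 value.

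**The case against.** The first part looks like a slip in code that the SAP offers only as an illustration. The prose of Sections 8.2 and 13.1 states the right rule, the lines just above build and sort `mcmc2`, and Section 13.1.1 uses it. A wrong number would require someone to re-sort the wrong file and ignore the one prepared for the step; even then the bias is conservative. The second part is disclosed in prose and code. For MAR eyes an own-arm draw agrees with Section 8.2, and the Visit 4 DCNVA value is still imputed 30 times. Section 8.2 does not name the predictors for control-based imputation, and withdrawn eyes with an observed Visit 3 value also keep their own value. The high missing rates are unlikely: 10% at Visit 4 uses up the whole assumed 12-month loss (51 of 501), and 5% of eyes with no data is about 25 eyes, half of it. The DCIVA figures depend on a visit list that the documents leave unclear.

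Much of this stands as to weight. The intended rule is clear, the variance is understated only in part, and the upper rows are outer limits. It does not remove the point. The printed co-primary code contradicts the prose and would not be expected to run. A drawn Visit 3 value also differs from an observed one: it is itself an imputation, and Section 8.2 requires multiple imputation, from control for physician-decision withdrawals. Disclosing the pre-step does not reconcile it with that rule.

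**Conclusion.** The concern holds on both parts and should be fixed before unmasking. The DCNVA code as printed does not produce the Section 8.2 estimate. The wrong dataset name is most likely carried over from the BCDVA block. If it were kept, it would pull -0.10 logMAR to no closer to zero than -0.090 at 10% missing, with no inflation of false superiority. The single draw understates the DCNVA standard error by well under 1% at 1% no-data eyes and by about 3% at the extreme, and leaves physician-decision withdrawals with no data only partly control-based.

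These sizes rest on assumed missing rates and on assumed correlations or slopes between Visits 3 and 4. Power stays above 99.9%, and no conclusion changes at the planned effect. BCDVA is essentially untouched because it has a baseline value. Sensitivity Analysis II inherits the pre-step for every unimplanted eye. The DCIVA error rates apply only if its first measurement is at Visit 4.

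**What to change.** 1. In the final DCNVA step, read `mcmc2` and list only the Visit 3, 4 and 5 variables.
2. Replace the single pre-draw. Hold eyes with no data out of the MCMC step, since they have no non-monotone gaps. Append them to each of the 30 MCMC datasets with a fresh first-visit draw in each: from the eye's own arm for MAR missingness, and from control for physician-decision withdrawals on DCNVA and DCIVA. The existing split and regressions then follow. Rewriting this step also removes a name mismatch in it: PROC MEANS writes `A3_stats`, but the data step merges `indata_stats`.
3. State the DCIVA visit list and give DCIVA its own imputation block. If it starts at Visit 4, the draw in item 2 supplies the Visit 4 value directly.
4. State that Sensitivity Analysis II uses the corrected step for unimplanted eyes.

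The cost is SAP code and wording; no new data are needed.
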